#### **Current Treatments:**

#### Limited therapeutic Options for Metastatic Melanoma

Cure rates for melanoma are high when the disease is discovered before it has spread from its primary location; however, metastasis frequently occurs, presenting a clinical challenge that has frustrated physicians and researchers alike for decades. Up until 2011, only two therapies were approved by the US food and drug administration (FDA) for the treatment of advanced (stage III or stage IV) MM. DTIC, the only chemotherapeutic licensed to treat MM was approved in 1975, has limited therapeutic utility. Patients on DTIC can expect a one-in-eight chance of having tumors shrink. Systemic therapy utilizing high-dose IL-2 was approved by the FDA in 1998. IL-2 is a naturally occurring glycoprotein secreted by T cells to mediate cellular immune response, and has been used as a cancer immunotherapy for almost 40 years. IL-2 mediates bystander activation and proliferation of CD4+ T-cell, CD8+ T-cell lymphocytes and to a lesser extent, NK cells. Although 4% of patients were cured using this immunological therapy, the side effects of systemic administration are significant and are fatal in 2% of patients. Even with these treatments, the outcome for patients with distant metastases is bleak, with median survival of 6 to 10 months and less than 5% of patients surviving for more than 5 years.

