#### Hypothesis:

*Hypothesis*: Pre-treatment with IL-2 in patients with highly suspicious pigmented lesions will reduce the incidence of metastatic melanoma compared to the PBS placebo group by initiating an adaptive immune response to native melanoma protein and peptide. *Major Aims*:

- 1) To conduct a pilot study to assess the number of patients needed to analyze in order to achieve a statistically significant differentiation between treatment and control outcomes in study measures including tumor infiltrating lymphocytes (TILs) and circulating immunomodulators.
- 2) To assess the efficacy of intralesional pre-treatment of IL-2 on highly suspicious lesions in generating an adaptive immune response and preventing melanoma metastasis.
- 3) Sub-study To assess if there a difference in specific immune modulators in patients receiving IL-2 pre-treatment compared to patients receiving a placebo.

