All blood, urine, and lesion biopsy samples will be labeled with a codified number (will not contain any patient identifying information) and will be immediately transported to [name] laboratory (Sir Charles Tupper Medical Building, 11F11) at Dalhousie University for storage. Fine needle aspiration of excised samples will be assessed for tumor genetic and epigeneitic profile (Figure 2). Blood and urine will be assessed for proteomic and metabolomic profiles, respectively (Figure 2).

A database containing patient IDs and codified numbers will be restricted to the office of [name] (11th floor, VG). This is a locked office, and the data will only be accessible to the investigators named on this application. This database for will contain patient IDs, and info on disease status, treatment/control, follow up visits, and sample analysis – only info pertinent to the outcome measures. All sample data will be assessed using codified descriptors and will contain no patient ID info. Once the RNA, proteomic, metabolomic and pathology data has been analyzed, unmasking treatment and control groups will be conducted at the VG office of [name], by the named investigators. If the data reaches statistically significance, the study will not accept any more patients, if not, a further 10 patients will be incorporated – to a maximum of 60 patients. Any publications of study results will be completed devoid of any information that could be used to identify patients included in the study.

All study participants will receive biannual assessments for 5 years after the initial intervention to assess disease progression, or the development of new melanoma, to compare between both treatment and control groups. There is no standardize test or measurable biomarker to assess established or lasting immunity. This aspect of the study is identical to the patient assessment conducted as per standard of care for melanoma patients. Again, any publications of study results will be completed devoid of any information that could be used to identify patients included in the study.

	Interleukin 2 Treatment Group				
Interleukin-2 Treatment Group		Placebo Treatment Group			

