Day 1 Clinical Visit -Area of skin suspected of cancer photographed. -IL-2 treatment administered -Blood sampled – 4 tablespoons (60 ml) -Urine Sampled – 3 to 4 tablespoons (50 ml)		Day 1 Clinical Visit -Area of skin suspected of cancer photographed. -Placebo administered -Blood sampled – 4 tablespoons (60 ml) -Urine Sampled – 3 to 4 tablespoons (50 ml)			
Day 8 Clinical Visit -IL-2 treatment administered		Day 8 Clinical Visit -Placebo administered			
Day 15 Clinical Visit -Area of skin suspected of cancer photographed. -Blood sampled – 4 tablespoons (60 ml) -Urine Sampled – 3 to 4 tablespoons (50 ml)		Day 15 Clinical Visit -Area of skin suspected of cancer photographed. -Blood sampled – 4 tablespoons (60 ml) -Urine Sampled – 3 to 4 tablespoons (50 ml)			
-Surgical excision		-Surgical excision			
Confirmed melanoma patients -Follow up every 6 months for 5 years					
	
 
-Area of skin suspected of cancer photographed.
 
-IL-2 treatment administered
 
-Blood sampled – 4 tablespoons (60 ml)
 
-Urine Sampled – 3 to 4 tablespoons (50 ml)
 
 Day 8 Clinical Visit 
 
-IL-2 treatment administered
 
 Day 15 Clinical Visit 
 
-Area of skin suspected of cancer photographed.
 
-Blood sampled – 4 tablespoons (60 ml)
 
-Urine Sampled – 3 to 4 tablespoons (50 ml)
 
 Surgical excision Confirmed	
 
-Area of skin suspected of cancer photographed.
 
-IL-2 treatment administered
 
-Blood sampled – 4 tablespoons (60 ml)
 
-Urine Sampled – 3 to 4 tablespoons (50 ml)
 
 Day 8 Clinical Visit 
 
-IL-2 treatment administered
 
 Day 15 Clinical Visit 
 
-Area of skin suspected of cancer photographed.
 
-Blood sampled – 4 tablespoons (60 ml)
 
-Urine Sampled – 3 to 4 tablespoons (50 ml)
 
 Surgical excision Confirmed mela			

		Clinical and	Sub-s	study	Procedures
	Interleukin-2/Placebo Treatment Group			Sub-Study Process/Procedures	
Clinical Trial Procedures		Day 1 Clinical Visit -Area of skin suspected of cancer photographed -IL-2/Placebo treatment administered -Blood sampled – 4 tablespoons (60 ml) -Urine Sampled – 3 to 4 tablespoons (50 ml)			Day 1 Clinical Visit -Blood sample – To be used in proteomic sub- study (study of protein levels found in blood) -Urine Sample – To be used in metabolomic sub- study (study of metabolites released in urine)

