#### Analysis of Data

#### Outcome measure/study objectives:

Assessment of Number of Patients Needed to Obtain Significance [**Time Frame: 1 year**] – Data will be analyzed in order to achieve a statistically significant differentiation between treatment and control outcomes in study measures including tumor infiltrating lymphocytes (TILs) and circulating immunomodulators.

Assessment of Metastasis [**Time Frame: 5 years**] - All patients will receive assessments every 4 months for 2 years and then biannual assessments for years 3-5 after the initial intervention to assess disease metastasis in treatment and control groups. Both number of new metastases (integer value) and thickness (mm) will be measured as a part of this assessment.

Sub-Study Outcome Measure:

Assessment of RNA genetic profile **[Time Frame: 5 years]** - RNA analysis of excised tissue will be compared to unaffected patient tissue obtained from the clear margins of the excisional biopsy to assess genetic changes resulting from the melanoma and treatment/placebo injections. RNA analysis will occur at [name] laboratory (Sir Charles Tupper Medical Building, 11F11) at Dalhousie University.

Assessment of Systemic Immune Response: Proteomic Analysis [**Time Frame: 5 years**] - Proteomic analysis will be conducted on blood samples to assess systemic immune response to both treatment and control groups. Serum collected from patient blood samples will be used for proteomic analysis to assess protein expression, including circulating immunomodulators (cytokines and chemokines) before, and after, treatment. Proteomic analysis will occur at Dalhousie's Proteomics and Mass Spectrometric Core Facility located in the Life Sciences Research Institute. This study may serve to help develop diagnostic protocols and methods of assessing response to treatments.

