#### How will the data be analyzed:

All study practices and statistical methods are based on the International Conference on Harmonization (IHC) document "Statistical Principles for Clinical Trials." Data will be summarized by treatment group. Baseline characteristic, safety outputs and a total overall column will be included to summarize all subjects. For all baseline, demographic, safety and efficacy outputs data will be summarized by treatment group. In summary tables of continuous variables, the minimum and maximum statistics, the arithmetic mean and median, the 95% confidence interval, standard deviation, and standard error will be presented will to the same number of decimal places as the original data. In summary tables of categorical variables, counts and percentages will be used. The denominator for each percentage will be the number of subjects within the population treatment group unless otherwise specified. All hypothesis testing will be carried out at the 5% (2-sided) significance level unless otherwise specified. P-values will be rounded to three decimal places. P-values less than 0.001 will be reported as <0.001 in tables.

The treatment label for all tables, listings and figures will be:

Treatment	Label
2 treatment cycles of	IL-2
500,000 IU of IL-2 in 0.1	Treatment
mL	
0.1 mL of sterile saline	Placebo
(0.9% m/v)	
All Treatments	Total

Where that any of the statistical methods described herein prove unsuitable during analysis, more appropriate methods will be used. All changes in methodology will be documented in the clinical study report. Additional ad-hoc analyses may be conducted as deemed suitable.

Subject inclusion/exclusion criteria will be determined at baseline visit, and subjects who do not meet all criteria will not be entered into the study. Those subjects deemed eligible to participate will be allocated a 3-digit number at randomization prior to the initial treatment. If a subject is discontinued at any time after entering the study, the Investigator will ensure this does not affect the patient's standard of care. At the patients request all unused biological samples (blood, urine, and core biopsies) will be immediately destroyed. The reasons for withdrawal will be recorded on the CRF and will be included in the final report. Failure to complete both (2) treatment cycles will result in patient removal from the trial.

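### The hypothesis is about the incidence of metastatic melanoma, but the plan names only a lesion count and a thickness, with no patient-level endpoint and no rule for death or unequal follow-up

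*Combined protocol and SAP*

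**What the plan says.** The Hypothesis section states that pre-treatment "will reduce the incidence of metastatic melanoma compared to the PBS placebo group". The section Outcome measure/study objectives, under Assessment of Metastasis with a five-year time frame, describes the measurement: "Both number of new metastases (integer value) and thickness (mm) will be measured as a part of this assessment".

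The section How will the data be analyzed is generic. It says "For all baseline, demographic, safety and efficacy outputs data will be summarized by treatment group", lists summary statistics for continuous variables (mean, median, SD, 95% CI and others) and counts with percentages for categorical ones, and adds "All hypothesis testing will be carried out at the 5% (2-sided) significance level unless otherwise specified". It names no test or model for metastasis.

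Three places describe the follow-up that would supply the data:

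- Outcome measure/study objectives: "All patients will receive assessments every 4 months for 2 years and then biannual assessments for years 3-5 after the initial intervention".
- Research Plan, text: "All study participants will receive biannual assessments for 5 years after the initial intervention to assess disease progression, or the development of new melanoma".
- Research Plan, procedure figures: "Confirmed melanoma patients -Follow up every 6 months for 5 years".

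No section defines the proportion of patients with a metastasis, time to first metastasis, metastasis-free survival or overall survival. None says how a death, a withdrawal or a loss to follow-up affects the count.

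**The concern.** Incidence is a property of patients: each one either develops metastatic disease or does not, at some date. A number of new metastases is a property of lesions, and it depends on how many arise in each affected patient and on how long that patient is observed. A by-arm summary of the count therefore answers a different question from the hypothesis.

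Three difficulties follow if the count is summarised as it stands. Lesions in one patient are not independent, so a single patient can decide the comparison. Counting stops at death, and the Limited therapeutic Options section quotes "median survival of 6 to 10 months" for patients with distant metastases, against a five-year window. Counting also stops for people who leave: Participant consent says no new information is collected after withdrawal without permission, and the analysis section removes patients who do not complete both treatment cycles.

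Thickness is a separate problem. The plan does not say whether it belongs to a metastasis or to a new primary. Either way it exists only for patients who develop such a lesion after randomisation, so a comparison by arm is not a randomised contrast.

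The Research Plan lets the investigators unmask the arms once the laboratory and pathology data are analysed. That can be well before five years, so an undefined metric could be chosen with the arms known.

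**Working it through.** **1. Is there a figure to reproduce?** No. The plan's only sample-size figure is 20 patients (10 per arm), extendable to 60. It comes without a named endpoint, effect size or event rate, so it cannot be tied to metastasis.

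**2. Expected number of cases.** The Background Information section gives 5-15% of melanoma patients progressing to stage IV.

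- 10 per arm: 10 × 0.05 = 0.5 to 10 × 0.15 = 1.5.
- 30 per arm: 30 × 0.05 = 1.5 to 30 × 0.15 = 4.5.

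A patient with k lesions moves the arm mean by k/n. One patient with five lesions weighs as much as five patients with one each, which is more than the whole expected number of cases per arm.

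**3. Effect of survival on countable time.** Assume exponential survival, so h = ln 2 / median. Mean countable years after spread, with five years remaining, are (1 − e^(−5h))/h.

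- Median 6 months: h = 1.386, giving 0.72 years.
- Median 10 months: h = 0.832, giving 1.18 years.

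The ratio is 0.72/1.18 = 0.61. At the same lesion rate, the group with shorter survival accrues 39% fewer later lesions.

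**4. Effect on the mean count per randomised patient.** Assume the same incidence p = 0.15 in both arms, onset uniform over five years, one lesion at onset and then λ = 2 new lesions per year, and median survival of 6 months in one arm and 10 in the other. Mean countable time is E = (1/h)[1 − (1 − e^(−5h))/(5h)], which is 0.617 and 0.918 years. The mean count is p(1 + λE).

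- Shorter survival: 0.15 × (1 + 2 × 0.617) = 0.335.
- Longer survival: 0.15 × (1 + 2 × 0.918) = 0.425.

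The arm with worse survival is 21% lower (0.335/0.425 = 0.79) although incidence is identical. The reduction is 16% at λ = 1 and 26% at λ = 4, and does not depend on p.

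**5. Bias against sampling error.** The bias in step 4 is 0.425 − 0.335 = 0.09 lesions per patient. Simulating the same scenario, the SD of the between-arm difference in mean count is about 0.53 at 10 per arm and 0.30 at 30 per arm. The bias is about 0.17 and 0.30 of one SD, so imprecision dominates.

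**6. What a patient-level endpoint can deliver.** At two-sided 5% and 80% power (normal approximation, pooled variance under the null), halving incidence needs 906 per arm from 5% or 278 per arm from 15%. For time to event with an assumed hazard ratio of 0.5, Schoenfeld's formula gives 4(1.960 + 0.842)²/(ln 0.5)² = 65.3, so 66 events. With 60 × 0.15 = 9 events, power is Φ(√9/2 × 0.693 − 1.960) = Φ(−0.92), about 18%. One case in 10 patients has an exact 95% CI of 0.3% to 44.5%.

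**7. Follow-up passages side by side.**

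| Place | Who | When |
|---|---|---|
| Outcome measure/study objectives | all patients | every 4 months for 2 years, then twice a year |
| Research Plan, text | all participants | twice a year for 5 years |
| Research Plan, figures | confirmed melanoma only | every 6 months for 5 years |

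These cannot all hold. They determine the denominator and the dates on which metastases can be detected.

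**The case against.** The strongest reply is that nothing is lost. A patient with a count of one or more is an incident case, so incidence is contained in the count. The analysis section already provides counts and percentages with the treatment group as denominator. The count and thickness are described as part of an assessment of metastasis, and the Research Plan text compares progression and new melanoma between arms. Metastasis also does not drive the decision to stop or extend enrolment, which follows the laboratory and pathology results.

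Much of this stands. A reader might infer that the plan cannot measure incidence at all. It can: what is missing is the definition and the analysis, not the data. But no section says that the count will be reduced to a yes/no per patient, and the clause allowing more suitable methods to be substituted makes it more important to settle this in advance.

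A reader might also infer that the plan makes patients who die early look better, or that the result will point the wrong way. The documents do not support that. No comparison of raw counts is specified. A patient who dies after spread still scores at least one, and so looks worse than every metastasis-free patient and better only than longer survivors with metastases. The bias is conditional on a raw-count comparison and is smaller than the sampling error. Likewise, no comparison of thickness by arm is stated; the supportable point is that its meaning is unclear and that such a comparison should be ruled out.

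**Conclusion.** The point holds as a gap in definition and analysis that should be closed. The hypothesised quantity is incidence; the only named measure is a lesion count and a thickness, with generic summaries and no treatment of death or unequal follow-up. With 0.5-4.5 expected cases per arm, one patient can decide a mean count. In the illustration a survival difference alone lowers the count by 16-26% at equal incidence.

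That illustration rests on assumptions: the lesion rates, the onset pattern, exponential survival and the difference in survival between arms are not in the documents. The 6-10 month median is for distant metastases, whereas the outcome is not restricted to distant spread. The 5-15% rate is for diagnosed melanoma, whereas enrolment is on suspicious lesions before diagnosis, so the trial's own rate may differ. Redefining the endpoint will not make 20-60 patients informative about metastasis. It makes the descriptive result answer the stated question, which matters for a pilot meant to inform a larger trial.

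**What to change.** Make the metastasis outcome patient-level, and fix it in the plan before any unmasking:

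- Report the number of patients with at least one metastasis out of all randomised, by arm, with exact 95% CIs.
- Report time from randomisation to first metastasis or death from any cause, by arm with Kaplan-Meier curves, censored at the last assessment. Report deaths without metastasis separately as well.
- Report new primary melanomas separately from metastases.
- State which lesion the thickness refers to. List lesion counts and thickness per patient, as description only, with no comparison of thickness between arms.
- Reconcile the three follow-up passages on who is assessed and when.

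The cost is a little more analysis work and revised wording. The Research Plan's database already holds disease status and follow-up visits. Vital status must be recorded; no section says that it is. With so few events, the result should be labelled descriptive.

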#### How will the data be analyzed:

All study practices and statistical methods are based on the International Conference on Harmonization (IHC) document "Statistical Principles for Clinical Trials." Data will be summarized by treatment group. Baseline characteristic, safety outputs and a total overall column will be included to summarize all subjects. For all baseline, demographic, safety and efficacy outputs data will be summarized by treatment group. In summary tables of continuous variables, the minimum and maximum statistics, the arithmetic mean and median, the 95% confidence interval, standard deviation, and standard error will be presented will to the same number of decimal places as the original data. In summary tables of categorical variables, counts and percentages will be used. The denominator for each percentage will be the number of subjects within the population treatment group unless otherwise specified. All hypothesis testing will be carried out at the 5% (2-sided) significance level unless otherwise specified. P-values will be rounded to three decimal places. P-values less than 0.001 will be reported as <0.001 in tables.

The treatment label for all tables, listings and figures will be:

Treatment	Label
2 treatment cycles of	IL-2
500,000 IU of IL-2 in 0.1	Treatment
mL	
0.1 mL of sterile saline	Placebo
(0.9% m/v)	
All Treatments	Total

Where that any of the statistical methods described herein prove unsuitable during analysis, more appropriate methods will be used. All changes in methodology will be documented in the clinical study report. Additional ad-hoc analyses may be conducted as deemed suitable.

Subject inclusion/exclusion criteria will be determined at baseline visit, and subjects who do not meet all criteria will not be entered into the study. Those subjects deemed eligible to participate will be allocated a 3-digit number at randomization prior to the initial treatment. If a subject is discontinued at any time after entering the study, the Investigator will ensure this does not affect the patient's standard of care. At the patients request all unused biological samples (blood, urine, and core biopsies) will be immediately destroyed. The reasons for withdrawal will be recorded on the CRF and will be included in the final report. Failure to complete both (2) treatment cycles will result in patient removal from the trial.

Data resulting from our RNA, metabolomic and proteomic studies will be analyzed using specific statistical software available to us at Dalhousie University, including Bio-Rad qPCR machine and CFX manager statistical software for RNA analysis, and liquid chromatography-tandem mass spectrometry (LC-MS/MS) systems (QTRAP5500 by ABSciex) and bioinformatic analysis for metabolomic and proteomic studies.

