This study is a randomized, controlled, double-blind study. Patients with highly suspicious pigmented lesions will be randomly assigned by an algorithm to one of two groups: 1) treatment group patients will be treated intralesionally with IL-2 (Proleukin (Aldesleukin), Novartis Pharmaceuticals Canada Inc.) at a dose of 500,000 International Units (IU) (0.1ml) for 2 treatment cycles 1 week apart (Day 1 and Day 8) Figure 1; 2) control group patients will be treated intralesionally with sterilized sodium chloride (0.9%, m/v) (0.1ml) Figure 1. Randomization will be done at the pharmacy for each patient (generated by a Random Block algorithm). IL-2 (Proleukin) will be obtained from the Provincial Drug Distribution Program by the pharmacy, paid for by [name] research services account (please see budget attached). The pharmacy will prepare either IL-2 treatment (supplied as 1 x 0.8ml (4 million units) or injectable placebo (0.9% sodium chloride) supplied as 0.8ml). The syringes will be prepared by following aseptic technique in a biohazard hood. A 22-million unit vial of IL-2 will be reconstituted with 1.2ml of sterile water for injection and mixed gently. After drawing up 3.2ml of 5% dextrose in water and transferring to the IL-2 vial, the resulting concentration will be 5 million units/ml. 0.8ml of the IL-2 solution will then be drawn into a 3ml syringe. Expiry time of the reconstituted solutions is 48 hours at 4C. The pharmacy will assign a codified ID which will be provided along with the syringe with the patient name labeled as "Interleukin-2/Placebo" (thus blinding study to clinician and patient). As a pilot study, the principle of the design is to test the feasibility of proceeding to a larger and more expensive trial following the methodology and protocol proposed. As such there will be a minimum of 20 (10 treatment, 10 placebo) participants (up to a maximum of 60). It is estimated that statistical significance will be reached with 20 patients, however it is not reached after 20 patients, an additional 10 (5 treatment, 5 control) patients will be enrolled. If significance is still not reached after 30 patients, an additional 10 patients will be enrolled and so on up to a maximum of 60 patients. If after 60 patients, significance is not achieved then further recruitment under the current protocol would not be logical and therefore the methodology would need to be revised or study discontinued.

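### No IL-2 versus placebo difference or confidence interval is pre-specified, although the pilot's first aim is to size the separation between the arms

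*Combined protocol and SAP*

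**What the plan says.** The section on how the data will be analysed, under Analysis of Data, is in effect the whole statistical plan.

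- **Level of summary.** "For all baseline, demographic, safety and efficacy outputs data will be summarized by treatment group".
- **Continuous variables.** "In summary tables of continuous variables, the minimum and maximum statistics, the arithmetic mean and median, the 95% confidence interval", then the standard deviation and standard error. The text does not say which parameter the interval is for.
- **Categorical variables.** "In summary tables of categorical variables, counts and percentages will be used". No interval is mentioned.
- **Columns.** "The treatment label for all tables, listings and figures will be" is followed by three labels: IL-2 Treatment, Placebo and Total. There is no column for a difference.
- **Between-arm output.** "All hypothesis testing will be carried out at the 5% (2-sided) significance level unless otherwise specified", with p-values given to three decimals.

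On purpose, the first of the Major Aims is "To conduct a pilot study to assess the number of patients needed to analyze" so that treatment and control can be separated on TILs and circulating immunomodulators. The outcome list in Analysis of Data repeats this as its first item. The Research Plan adds that "the principle of the design is to test the feasibility of proceeding to a larger and more expensive trial". It also sets the enrolment rule: at least 20 patients (10 per arm), then 10 more at a time until significance is reached, to a maximum of 60.

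**The concern.** Planning a larger trial needs the size of the between-arm difference and the range of differences still compatible with the data. A p-value gives neither. This plan commits to a p-value and to separate arm summaries, and nowhere to the contrast itself. No section plans a difference, ratio or hazard ratio, or an interval for one, for TILs, immunomodulators or metastasis.

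What is at stake is the pilot's main deliverable. If the contrast is chosen only after unmasking, its form (means, ranks or proportions) can be chosen with the results in view. If it is not reported at all, the next trial is sized from a p-value or from a difference that each reader works out separately. A safety percentage of 0% with no interval can likewise look more reassuring than 10 patients allow.

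**Working it through.** The documents give no SD, event rate, target difference, power or test. Effects below are therefore in SD units and assume one normal endpoint, equal SDs and 1:1 allocation. N is fixed in steps 1 to 4; step 5 applies the plan's enrolment rule.

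**1. The plan's own figure.** The Research Plan estimates that 20 patients will reach significance. This cannot be reproduced, because no inputs are given. Working backwards at 80% power and two-sided 5%, 10 per arm detects (1.960 + 0.842) × √(2/10) = 1.25 SD by the normal approximation, or 1.33 SD by the t-test.

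**2. How strongly sizing depends on the difference.** Per-arm n = 2 × (1.960 + 0.842)² / d² ≈ 15.7 / d², rounded up.

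| True difference d | Per arm | Total |
|---|---|---|
| 0.5 SD | 63 | 126 |
| 0.8 SD | 25 | 50 |
| 1.0 SD | 16 | 32 |

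Halving the difference from 1.0 to 0.5 SD raises the total about fourfold.

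**3. What an interval for the difference would show.** Half-width = t(0.975, 2n − 2) × √(2/n).

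| Per arm | Calculation | Half-width |
|---|---|---|
| 10 | 2.101 × 0.447 | 0.94 SD |
| 20 | 2.024 × 0.316 | 0.64 SD |
| 30 | 2.002 × 0.258 | 0.52 SD |

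For example, an observed 0.5 SD at 10 per arm has t = 0.5 / 0.447 = 1.12, p = 0.28 and an interval of −0.44 to 1.44 SD. That is inconclusive: it spans no effect and a very large one.

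**4. Percentages.** For 0/10 the exact (Clopper-Pearson) upper limit is 1 − 0.025^(1/10) = 30.8%. For 5/10 the limits are 18.7% and 81.3%. For an assumed 0/10 versus 1/10 the Newcombe interval for the difference is −40 to +19 percentage points.

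**5. Effect of the enrolment rule on an ordinary interval.** A simulation of 200,000 trials tested one endpoint by t-test at 20, 30, 40, 50 and 60 patients, stopping at the first p < 0.05.

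| True difference | Significant at some look | Ordinary 95% interval at the stop covers the truth | Mean estimate among significant results |
|---|---|---|---|
| 0 | 12.8% | 87.2% | about 0 (errors in both directions cancel) |
| 0.5 SD | 57.4% | 94.9% | 0.84 SD |

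The coverage shortfall is shown at a true zero difference. At a true 0.5 SD, coverage is close to nominal, but the estimate among significant results is inflated.

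**The case against.** The strongest reply is that the information is not withheld. Arm means, SDs and SEs are planned, and so are counts. For a roughly normal outcome a reader can form the difference ± t × √(SE₁² + SE₂²), and intervals for percentages follow from the counts. Arm means and SDs are also the usual inputs for sizing. This stands, and it rules out the stronger reading that the pilot would report nothing about the effect except a p-value. What remains is that the contrast is not pre-specified. For ordinal or skewed measures the listed summaries do not yield a Hodges-Lehmann shift, which needs patient-level data.

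Four other inferences go further than the documents:

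- **That the interval is definitely for each arm's mean.** This is the natural reading of a by-group list with mean, SD and SE, but the parameter is not named. If the sponsor meant something else, the wording still needs correcting.
- **That the arms will be judged by whether their intervals overlap.** Nothing in the plan says so; significance decides.
- **That a non-significant result at 20 patients would be taken as no effect.** The rule then adds 10 patients. Lack of significance ends recruitment under this protocol only at 60.
- **That metastasis will appear as a bare percentage.** The hypothesis speaks of incidence, but the outcome list measures the number of new metastases and thickness in mm. No metastasis percentage is defined.

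The plan also cites ICH statistical principles and allows ad-hoc analyses. Neither commits the sponsor to an estimate or an interval.

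It is also fair to say that a contrast cannot be fully specified while the TIL scale and the test are unnamed. That affects the order of work and does not remove the gap.

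**Conclusion.** The concern holds as a gap in pre-specification. No between-arm estimate or interval is planned in any section, although the first aim and the pilot rationale depend on the size of the separation. The plan should be changed, at small cost.

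The missing interval would be wide: ±0.94 SD at 10 per arm and ±0.52 SD at 30 per arm, with an exact upper limit of 31% for 0/10. The SD figures rest on assumed normal data, equal SDs and fixed N; the exact limit needs only independent patients with a common risk.

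A reader might infer that an ordinary 95% interval, once added, could carry the pilot's conclusion. The enrolment rule does not support that. An interval that matches the test excludes zero whenever recruitment stops early. In the simulation, ordinary intervals covered a true zero about 87% of the time, and significant results averaged 0.84 SD when the truth was 0.5 SD.

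**What to change.** In the section on how the data will be analysed, add the following:

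1. For each main outcome (the TIL measure, circulating immunomodulators, metastasis), report IL-2 minus placebo with a 95% confidence interval suited to the outcome's stated scale: Welch for means, Hodges-Lehmann for ordinal or skewed measures, Newcombe for a difference in percentages. The scale of each outcome has to be stated first.
2. Give an exact 95% interval with every safety percentage.
3. Name the parameter of the existing by-group interval and keep it as description only.
4. Because enrolment stops on significance at 20, 30, 40, 50 or 60 patients, either compute the estimate and interval to allow for the repeated looks, or label them as unadjusted. In the second case, state that coverage of a true zero is about 87% (one normal endpoint, five looks) and that estimates are inflated after an early stop, and do not use them at face value for sizing.

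The cost is a few sentences and a few more table columns, with no new data, visits or patients. The downside is that wide intervals will make the pilot look less definite. Adjusting for the looks also means fixing in advance which outcome and test drive the stopping rule; labelling the interval as unadjusted avoids that work but gives a weaker basis for sizing.
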